14.1.3 Study Outcomes

The primary outcome for this study will be the combined number and incidence rate of several arrhythmias of interest that occur in each group over a 14 day period post-study drug. These arrhythmias including ventricular fibrillation, sustained ventricular tachycardia (≥ 125 BPM, ≥ 30 seconds), non-sustained ventricular tachycardia (≥ 125 BPM, ≥ 16 beats, < 30 seconds) and high degree AV block (2nd or 3rd degree, ≥ 8 beats) were chosen because they are significant

prognostic indicators of depressed left ventricular ejection fraction and cardiac death [1]. The combined number of arrhythmic events in each group will be calculated along with the arrhythmia incidence rate defined as the percentage of patients in each group experiencing at least one of the defined arrhythmias of interest.

An exploratory sub-analysis will be conducted to determine the number and incidence rate of each separate arrhythmia type per dose group.

Secondary exploratory efficacy outcomes will include:

Infarct size as a proportion of ventricular volume (INF/VV), the myocardial salvage index (MSI), absolute MI size (INF) at 72 +/- 24 hours and 3 months post study drug measured by CMR.

The proportion of patients with ST-segment resolution at 4 hours post study drug.

Serum levels of troponin calculated as AUC 0-48 hours post study drug.

Cardiac-related adverse events including the development of heart failure.

The incidence of all-cause and cardiac mortality out to 6 months post PCI.

In addition to the measurement of safety and efficacy parameters in this study, serum biomarker levels of cardiac injury, inflammation and remodeling will also be assessed.

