6 STUDY DESIGN

6.1 Primary Outcomes

The primary outcome for this study will be the combined number and incidence rate of several arrhythmias of interest for 14 days post-study drug. The arrhythmias of interest include the following categories:

- Ventricular fibrillation
- Sustained ventricular tachycardia (heart rate [HR] \geq 125 beats per minute [BPM], \geq 30 seconds)

- Non-sustained ventricular tachycardia (HR \geq 125 BPM, \geq 16 irregular beats, $<$ 30 seconds)
- High degree Atrioventricular (AV) block (2nd or 3rd degree, \geq 8 irregular beats)

The time-to-last-event outcome for each arrhythmia of interest will be studied.

The time-to-patch-applied, derived as time duration between the start of PCI procedure and the application of the patch monitoring device will also be studied.

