11.4.1 Primary Analysis (Safety)

Incidence Rate of Events

The primary outcome for this study will be the combined number and incidence rate of several arrhythmias of interest for 14 days post-study drug. The combined number of arrhythmic events in each treatment group will be calculated along with the arrhythmia incidence rate defined as the number of arrhythmia events of interest divided by the total person-time within each treatment group (or the overall FDY-5301 group), expressed as a percentage. The summarization will be presented by 2 separate periods within the 14-day monitoring duration, and also as overall. Period 1 will be the first 48 hours since the start of PCI and period 2 will be the remaining time of 14-day monitoring duration.

The same summarization method will be repeated after stratification of baseline TIMI flow (grade 1 and lower combined, or, grade 2 and 3 combined) and infarct type (anterior or other).

Person-time is an estimate of the time-at-risk in hours for all patients who contributed to the analysis population. The total person-time is calculated as the sum of recording time across patients during the 14 day monitoring period, within each treatment group (or the overall FDY-5301 group). The unit for person-time in this study is person-hours.

The number of arrhythmias of interest and its incidence rates will be summarized by treatment group and the overall FDY-5301 group.

The incidence rate ratio of each active treatment group (and overall) against the placebo group will be calculated.

As an exploratory sub-analysis, the summarization for the number of events and incidence rates will be repeated separately for each arrhythmia category as outlined in Section 6.1 and also separately for non-serious arrhythmias (ie, any arrhythmias which do not meet the criteria as outlined in Section 6.1).

The arrhythmia incidence rates (ie, arrhythmias per person-time) for each arrhythmia type will be summarized by treatment groups in hourly intervals. The intervals may be altered upon reviewing the actual data. Arrhythmia rates by time interval may also be presented in a graphical format.

Occurrence of reperfusion arrhythmias collected prior to use of the continuous rhythm monitoring device will be summarized according to categories as defined in the CRF.

Relationship between each arrhythmia type occurred within 48 hours of the start of PCI procedure and all-cause mortality may be evaluated depending on data availability.

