Time-to-Last-Event

The time-to-last-event is defined as the duration between the start time of PCI and the last occurrence of the arrhythmia event. The time-to-event will be censored for a subject if a subject does not experience any arrhythmias of interest before the end of the 14-day monitoring period or the date of early termination from the study. The censoring time will be at the last available time of arrhythmia monitoring.

Median and first and third quartiles of the time-to-last-event will be summarized for each treatment group and the overall FDY-5301 group for each arrhythmia of interest (and combined).

Kaplan-Meier curves will be presented by treatment, baseline TIMI flow, and infarct type for each arrhythmia of interest and also repeated separately for each arrhythmia category.

Time-to-Patch-Application

The duration between the start of PCI to the application of the patch will be derived and summarized by treatment group.

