11.5.1 Adverse Events

The study specifically recruits STEMI patients; therefore the myocardial infarction (MI) itself will not be characterized as an AE. However, complications arising as a consequence of the MI, for example, an emergent or worsening heart failure, death, or arrhythmias will be specifically documented as adverse events in the CRFs.

A baseline sign and symptom is defined as an AE that starts after the patient has provided written informed consent and that resolves prior to the first dosing occasion, or an AE that starts prior to the first dosing occasion and does not increase in severity after dosing. A treatment-emergent AE (TEAE) is defined as an AE that occurs postdose or that is present predose and becomes more severe postdose.

All AEs will be listed. The TEAEs will be summarized by treatment, severity, and relationship to the study drug. The frequency (the number of TEAEs, the number of patients experiencing a TEAE, and the percentage of patients experiencing a TEAE) of TEAEs and serious TEAEs will be summarized by treatment, and by MedDRA system organ class and preferred term. The summary and frequency TEAE tables will be presented for all causalities and for those TEAEs considered related to the study drug (those that have a relationship of probable or possible). A subset of serious adverse events and adverse events which are cardiac related, including the development of heart failure, will also be presented as summary tables. For any AEs that change severity ratings the AE will be included only once under the maximum severity rating in the summaries. Any life-threatening, severe or serious AEs will be listed.

Onset times postdose are calculated from the start of study drug infusion.

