13 CHANGES FROM THE PROTOCOL SPECIFIED STATISTICAL ANALYSES

For the analysis of arrhythmias of interest, a person-time adjustment will be applied to account for potential missing data during the 14-day monitoring period, due to possible unforeseen reasons such as patient withdrawal, device failure or death. The incidence rate for each treatment group (and overall FDY-5301) will be calculated as the number of events divided by the total person-time of monitoring within each treatment group. The incidence rate ratios of each treatment group (and overall FDY-5301) versus the placebo will be derived.

Scope of the interim analyses has been updated.

Overall summary for primary and exploratory safety and efficacy endpoints will be summarized by stratification of TIMI flow grade and infarct location

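### Time to last arrhythmia is censored as if it were time to first arrhythmia, so before day 14 fewer affected patients and longer-lasting arrhythmia both raise the Kaplan-Meier curve

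*SAP*

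**What the plan says.** SAP 6.1, under Primary Outcomes, adds to the arrhythmia counts and rates: "The time-to-last-event outcome for each arrhythmia of interest will be studied". SAP 11.4.1 defines this time as running from the start of PCI to the last arrhythmia. Its censoring rule is: "The time-to-event will be censored for a subject if a subject does not experience any arrhythmias of interest" by the end of the 14-day monitoring or early termination. For those patients, "The censoring time will be at the last available time of arrhythmia monitoring". Nobody else is censored, so a patient with any arrhythmia enters as an observed event at the last one recorded.

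Two outputs follow. One is the median and quartiles by group, for each arrhythmia of interest and combined. The other is graphical: "Kaplan-Meier curves will be presented by treatment, baseline TIMI flow, and infarct type for each arrhythmia of interest". The SAP does not say whether the medians are Kaplan-Meier estimates or are taken among affected patients only.

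The protocol's per-patient measure is "the percentage of patients in each group experiencing at least one of the defined arrhythmias of interest" (14.1.3). In SAP 11.4.1 the incidence rate is instead "the number of arrhythmia events of interest divided by the total person-time within each treatment group". SAP 13 gives the reason: "a person-time adjustment will be applied to account for potential missing data during the 14-day monitoring period". That adjustment applies to the rate and not to the last-event time.

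**The concern.** For a first event, an arrhythmia-free patient who leaves observation may still have the event later, so censoring is right. For a last event, a patient recorded for 14 days without arrhythmia has nothing outstanding within the window. Kaplan-Meier nevertheless carries that patient as still awaiting a last event. Never affected and affected until late then look alike for most of the plot, although one is a good result and the other a bad one.

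Protocol 14.1.4 says the study is meant to characterize arrhythmia over 14 days and to help find an endpoint for pivotal trials. A figure on which benefit and harm move the same way does not serve that aim. The proportion of patients affected would settle the reading, but the SAP text no longer plans it from the patch recordings. The adverse event tables count patients, but from a different source: "arrhythmias will be specifically documented as adverse events in the CRFs" (SAP 11.5.1).

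**Working it through.** **Inputs.** Endpoint, censoring rule and displays: SAP 11.4.1. Group sizes, 20 placebo and 60 combined FDY-5301: SAP 9. The documents give no incidence, last-event timing or early-stop rate (Protocol 14.1.4 says little data exist), so these are assumptions shown over a range. The plan states no figure for this outcome, so there is none to reproduce.

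**Formula.** With complete recording, all censoring falls at day 14 (336 h). Before then

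S(t) = 1 - p*F(t).

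A lower p and a later F both raise S(t). At day 14, F = 1 and S = 1 - p whatever the timing. Plotting 1 - S does not help, because both changes then lower it.

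**Hand example, 20 patients per group.**

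| Group | Day 2 | Day 4 | Day 7 | Day 14 |
|---|---|---|---|---|
| 8 affected, last events days 0.5-4 | 0.80 | 0.60 | 0.60 | 0.60 |
| 4 affected, same timing | 0.90 | 0.80 | 0.80 | 0.80 |
| 8 affected, last events days 4-13 | 1.00 | 0.95 | 0.85 | 0.60 |

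Up to day 7 the longer-lasting group lies above even the group with half as many affected.

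**Range of incidence.** Take F(t) = (1 - exp(-t/m)) / (1 - exp(-336/m)). With m = 48 h the median among affected patients is 33 h and F(48) = 0.633. With m = 100.2 h the median is 66 h and F(48) = 0.394. At 60% affected, placebo is 1 - 0.6 x 0.633 = 0.62, halved incidence is 1 - 0.3 x 0.633 = 0.81, and prolongation is 1 - 0.6 x 0.394 = 0.76.

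| Affected on placebo | Placebo S(48 h) | Incidence halved | Median prolonged to 66 h |
|---|---|---|---|
| 60% | 0.62 | 0.81 | 0.76 |
| 40% | 0.75 | 0.87 | 0.84 |
| 20% | 0.87 | 0.94 | 0.92 |

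The Kaplan-Meier median exists only if S reaches 0.5, that is, if at least half are affected.

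**Chance in groups of 20 and 60.** With complete recording S(48 h) is a simple proportion, so exact binomial probabilities apply. At 60% affected, the active curve lies above placebo in 94% of trials with halved incidence and 87% with prolongation to 66 h, against 47% with no effect. At 20% affected the figures are 74%, 67% and 44%.

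**Alternative curve.** The proportion of all patients whose last arrhythmia falls after t is p*(1 - F(t)). At 48 h and 60% affected it is 0.6 x 0.367 = 0.22 on placebo, 0.3 x 0.367 = 0.11 with halved incidence and 0.6 x 0.606 = 0.36 with prolongation. Benefit and harm now move in opposite directions.

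**Early stops.** Assume recording stops between 48 and 168 h and each affected patient has 1 + Poisson(2) events. If last-event times follow the 33 h distribution, with earlier events uniform before them, the median among affected patients falls from 33.2 h to 32.7, 32.3 and 31.1 h when 10%, 20% and 50% stop early. If the 48 h exponential instead applies to each event, it falls from 72.3 h to 69.2, 66.2 and 58.4 h.

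Censoring early-stopped patients on the alternative curve has its own effect. With 20% stopping after 48 h, its value at 48 h is 1 - 0.8 x (1 - 0.22) = 0.38 instead of 0.22, because those patients are all held as not yet at their last event.

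**The case against.** The strongest reply is that little hangs on this figure. Protocol 14.1.6 makes the primary safety outcome descriptive with no hypothesis tested, and the event counts and person-time rates do not use the censoring rule. SAP 11.4.1 also plans rates for the first 48 hours and the remainder, and in hourly intervals by arrhythmia type. Prolonged arrhythmia should raise the late intervals, and prevention should lower the counts. The curve's own level near day 14 shows the proportion affected. The table shells, which are not part of these documents, may print event and censored counts. All of this stands and limits the harm. It does not make the curve readable before day 14, and the planned rates are event-level, so one patient with many episodes can dominate them.

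The size can also be challenged. Curves for single arrhythmia categories sit at or below the combined incidence. At 20% affected the gaps at 48 h are 0.05 to 0.06, about one patient in 20. That stands too: the direction is algebra, but the size depends on an incidence nobody has stated.

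A reader might infer that the primary outcome is invalid or that a false claim of benefit would follow. The documents do not support that, since no test is planned on these curves. Nor do they show that the medians are wrong: if taken among affected patients only, they avoid the problem. A large bias from early stopping is not shown either. Under the model matching the main scenario the shift is at most about 2 h, and it is larger only under a different event model.

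**Conclusion.** The point holds as a defect of a descriptive display. The rule for time to last arrhythmia makes prevention and prolongation raise the Kaplan-Meier curve alike before day 14. This direction follows from the definition with complete recording and needs no assumed rate. Under the assumed timings the rise at 48 h is 0.14 to 0.19 at 60% affected and about 0.05 to 0.06 at 20%. Counting early-stopped affected patients as fully observed is a secondary weakness whose size cannot be settled from the documents.

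**What to change.** **(a) Replace the curve.** Plot the proportion of all patients whose last arrhythmia falls after time t, with fully monitored arrhythmia-free patients at time 0. Any patient whose recording ends early, affected or not, is censored at the end of recording and not counted as observed. Tabulate these patients separately, deaths included, with their last recorded event. This censoring pushes the curve up, as the 0.38 against 0.22 above shows, so plot beside it the same curve for patients with complete recording. The censored curve can never lie below that one. Read direction from the complete-recording curve, which assumes that early stopping is unrelated to arrhythmia. Use the distance between the two to show how much the missing recordings matter.

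**(b) Report the parts separately.** Give by group the proportion with at least one arrhythmia of interest on the patch. State that the median and quartiles are descriptive and are taken among affected patients whose recording reached a stated tolerance around day 14. The visit window of +/- 2 days in Protocol 5.5.6 is one choice, with the planned patch swaps allowed.

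A time-to-first-arrhythmia curve with the present censoring rule is optional. If added, it must note that patch recording starts only once the device is affixed.

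**Cost.** One SAP paragraph plus table and figure shells, with no new data. The summary in (b) conditions on being affected and on completing monitoring, in groups of about 20 evaluable patients (80/4) or up to about 40 in the ITT population (160/4), so it is not a randomized comparison.

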11.4.2 Secondary Efficacy Analysis

11.4.2.1 Infarct Size Parameters from CMR

INF/VV, MSI, and INF will be assessed by CMR at 72 ± 24 hours post-study drug and 3 months post-study drug. Summary statistics for the observed values along with changes from baseline will be produced for each treatment group and the overall FDY-5301 group for each parameter. The baseline is defined as the measurement taken at the 72 hour timepoint.

For the changes from baseline for each of these parameters, a single pairwise comparison will be performed to analyze the results between all three FDY-5301 groups (overall) and placebo at both the 3 months post-study drug timepoints. An unpaired Student's T-test will be used for the pairwise comparison if the data are normally distributed and a Mann-Whitney rank test will be used for nonparametric data. Normality will be assessed based on the Shapiro-Wilk test at the 5% level. If the unpaired Student's T-test was selected, the difference in means and its 95% confidence interval will be produced.

Each treatment group will also be tested using a one-way analysis of variance (ANOVA) to obtain a common variance followed by a Dunnett's post-test to separately compare each FDY-5301 dose group to placebo.

The same summarization method and statistical analyses will be repeated by baseline TIMI flow (grade 1 and lower, or, grade 2 and 3) and infarct type (anterior or other).

The changes from baseline in infarct size parameters may be compared between treatment groups in the form of a frequency table as necessary. The definition for these changes from baseline categories will be determined at a later stage based on the actual data.

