4 INTRODUCTION

This SAP has been developed after review of the clinical study protocol Final Version 1.0 dated 02 April 2017 and Final Version 2.0 dated 21 August 2017.

This SAP describes the planned analysis of the safety, efficacy, and PK data from this study. A detailed description of the planned TFLs to be presented in the Clinical Study Report (CSR) is provided in the accompanying TFL shell document. In general, the analyses are based on information from the protocol, unless they have been modified by agreement between Faraday Pharmaceuticals and Covance Early Clinical Biometrics. A limited amount of information concerning this study (eg, objectives, study design) is given to help the reader's interpretation. This SAP must be finalized prior to the lock of the clinical database for this study. When the SAP and TFL shells are agreed upon and finalized, they will serve as the template for this study's CSR.

This SAP supersedes the statistical considerations identified in the protocol; where considerations are substantially different, they will be so identified. If additional analyses are required to supplement the planned analyses described in this SAP, they may be performed and will be identified in the CSR. Any substantial deviations from this SAP will be agreed upon between Faraday Pharmaceuticals and Covance Early Clinical Biometrics and identified in the CSR.

This SAP is written with consideration of the recommendations outlined in the International Conference on Harmonisation (ICH) E9 guideline entitled, "Guidance for Industry: Statistical Principles for Clinical Trials" and the ICH E3 guideline entitled, "Guidance for Industry: Structure and Content of Clinical Study Reports."^{1,2}

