9 SAMPLE SIZE JUSTIFICATION

As this is the first clinical study of FDY-5301 in patients, safety is the primary focus. For this reason, the goal is to expose a limited number of patients to FDY-5301 while still powering the study to detect significant differences in efficacy measures across groups. A total sample size of 80 patients will provide 80% power to detect a 37% reduction in infarct size (INF) / ventricular volume (VV) assuming a standard deviation (SD) of 10%, a 24% increase in MSI assuming a SD of 20% and a 39% reduction in Troponin area under the curve (AUC) with an SD of 60%. Equal variance was assumed among groups with an unbalanced allocation of patients to placebo (n = 20) and overall FDY-5301 treatment groups (n = 60).

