11.4.2.4 Measures of Cardiac Function by CMR

The EDV, ESV, FS and EF will be assessed at 72 ± 24 hours post-study drug and 3 months post-study drug.

Summary statistics will be produced for the observed values along with changes from baseline by each treatment group and the overall FDY-5301 group for each parameter. The baseline is defined as the measurement taken at the 72 hour timepoint.

For the changes from baseline for each of these parameters, a single pairwise comparison will be performed to analyze the results between all three FDY-5301 groups (overall) and placebo. An unpaired Student's T-test will be used for the pairwise comparison if the data are normally

distributed and a Mann-Whitney rank test will be used for nonparametric data. Normality will be assessed based on the Shapiro-Wilk test at the 5% level. If the unpaired Student's T-test was selected, the difference in means and its 95% confidence interval will be produced.

The parameters from each group will then be tested using a one-way ANOVA to obtain a common variance followed by a Dunnett's post-test to separately compare each FDY-5301 dose group to placebo.

The same summarization method and statistical analyses will be repeated by baseline TIMI flow (grade 1 and lower, or, grade 2 and 3) and infarct type (anterior or other).

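### The CMR outcomes are tested as change from a post-treatment scan, so an infarct-size effect already present at 72 hours cancels and the stated power does not apply

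*SAP*

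**What the plan says.** SAP 11.4.2.1 covers INF/VV, MSI and INF, measured by CMR at about 72 hours and at 3 months. Observed values and changes are both summarised, but the pooled test is tied to the changes: "For the changes from baseline for each of these parameters, a single pairwise comparison will be performed to analyze the results". The arms and the time of that test are then given as "between all three FDY-5301 groups (overall) and placebo at both the 3 months post-study drug timepoints". The reference point is fixed by "The baseline is defined as the measurement taken at the 72 hour timepoint". The t-test or Mann-Whitney choice, and the difference in means with its 95% confidence interval, belong to that comparison.

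The dose-level step follows: "Each treatment group will also be tested using a one-way analysis of variance (ANOVA) to obtain a common variance", then Dunnett. It does not name the variable analysed.

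SAP 11.4.2.4 sets the same 72-hour baseline and the same pooled test on change for EDV, ESV, FS and EF. Its dose-level sentence reads "The parameters from each group will then be tested using a one-way ANOVA", which could mean values or changes.

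SAP 9 claims "80% power to detect a 37% reduction in infarct size (INF) / ventricular volume (VV) assuming a standard deviation (SD) of 10" percent, together with 80% power for a 24% increase in MSI (SD 20%), at 20 placebo and 60 pooled FDY-5301 patients. It mentions neither a change score nor an SD of change.

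The protocol (4.2, 11 and 14.1.6) compares these outcomes between groups at both times and defines no 72-hour baseline.

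**The concern.** A baseline should precede treatment. Here the drug is given between an hour and 5 minutes before reperfusion (Protocol 5.1), and the first CMR comes 48–96 hours after it (Protocol Table 2, footnote 7). The 72-hour scan is therefore a result of treatment, and infarct size on it is a listed outcome. The general rule in SAP 11.1.1 takes the last pre-dose value, so the CMR sections make an express exception.

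The drug is meant to limit reperfusion injury and so produce a smaller infarct (Protocol 3.1, 3.3). That effect could well be visible by 72 hours, and it is the effect the change score removes. INF/VV and MSI are two of the three outcomes behind the power statement, and the primary outcome carries no hypothesis test (Protocol 14.1.6). As written, a real benefit could be reported as no difference, or as a difference favouring placebo.

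**Working it through.** **1. The plan's own figure.** Inputs from SAP 9: n = 20 and 60, INF/VV SD 10, power 80%. Assumed: two-sided 5%, SD in percentage points, relative effects (read as absolute points, power would exceed 99% for both CMR outcomes).

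- Standard error = 10 × √(1/20 + 1/60) = 2.58 points.
- Noncentral t, 78 df: detectable difference 7.32 points.
- For this to be a 37% reduction, the placebo mean must be 7.32 / 0.37 = 19.8%. I use 20%, so the effect is 0.37 × 20 = 7.4 points; power 80.8%.
- MSI: 14.65 points (SD 20); 14.65 / 0.24 = 61.0% placebo mean.

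The documents give no placebo mean, alpha or sidedness. One-sided 5% would imply an INF/VV placebo mean of 17.5%. The troponin figure (39%, SD 60%) has 70% power two-sided and 80% one-sided, so the intended sidedness is unclear.

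**2. What the change score estimates.** Let d72 and d3 be the treatment effects at 72 hours and 3 months.

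- Expected difference in change = d3 − d72.
- SD of change = 10 × √(2(1 − ρ)) = 10.0, 7.7, 6.3 and 4.5 at ρ = 0.5, 0.7, 0.8 and 0.9.

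If the effect is maintained, or both arms shrink by the same number of points, d3 − d72 = 0 at any ρ. Power for benefit is then 2.5%. A 20,000-run simulation at ρ = 0.8 of a maintained effect at the normal-approximation detectable size (0.723 SD) gave 4.9% significance in both directions together for the change test, and 79% for the 3-month value.

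**3. Proportional shrinkage.** If both arms shrink by a fraction s, d3 = (1 − s) × d72. Active minus placebo change in INF/VV is +7.4s, opposite in sign to the benefit. Chance of significance in the wrong direction:

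| s | Difference | ρ = 0.5 | 0.7 | 0.8 | 0.9 |
|---|---|---|---|---|---|
| 10% | +0.74 | 4.7% | 5.5% | 6.5% | 9.2% |
| 20% | +1.48 | 8.2% | 11.0% | 14.3% | 24.4% |
| 30% | +2.22 | 13.3% | 19.4% | 26.9% | 47.6% |

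If the 3-month SD shrinks too, the ranges are 4.8–9.5%, 9.0–24.4% and 15.8–42.5%.

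**4. Effect arising partly after 72 hours** (no proportional shrinkage). Change-score power over ρ = 0.5–0.9 is 5–9% if 10% of the 7.4 points arises late, 11–35% if 25% does, and 29–89% if 50% does. Reaching 80% needs 7.3, 5.7, 4.6 or 3.3 late points at the four correlations, which is 99% down to 44% of the effect.

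**5. Observed 3-month values under proportional shrinkage.** Power stays at 81% if the SD shrinks with the mean. If the SD stays at 10, it is 72%, 62% and 51% at s = 10%, 20% and 30%.

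**6. The texts side by side.** The timepoint phrase in SAP 11.4.2.1 announces two times and names one. A change from 72 hours exists only at 3 months, so a 72-hour comparison may have been lost in drafting. Protocol 14.1.5 schedules MSI, INF/VV and INF after the day-14 visit, when only the 72-hour values exist and no change can be computed. SAP 11.6.8 itself plots observed INF/VV at 3 months against exposure. SAP 4 promises that "where considerations are substantially different, they will be so identified". SAP 13 lists the person-time adjustment, the interim scope and the stratified summaries, but no change of tested variable.

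**The case against.** The strongest reply is that this is a drafting slip in secondary, exploratory analyses. The timepoint phrase is visibly damaged, the ANOVA/Dunnett variable is open, and observed summaries by arm would let a reader recover the unadjusted comparison. That is fair, but recovering it is not a prespecified test, and a dose-by-dose Dunnett step does not replace the pooled one.

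Four narrower points stand in part:

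- **Disclosure.** The SAP cites protocol versions dated 02 April and 21 August 2017; the protocol supplied is dated 30 August 2017. The omission from SAP 13 is shown only against the latter.
- **Timing.** SAP 12 moves the CMR analysis to after the 3-month visit, and SAP 13 says "Scope of the interim analyses has been updated". That discloses the timing, not the switch to change scores.
- **Remodeling.** Change from an early scan to 3 months is a legitimate question for EDV, ESV, FS and EF. Later effects stay in the change score, none of these four is a powered outcome, and I claim no sign reversal for them. Effects already present at 72 hours still cancel.
- **Inputs.** Shrinkage, correlation and effect timing are assumed. The 81% follows from a placebo mean derived from the plan's own 80%, so it shows consistency and is not independent support.

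**Conclusion.** The concern holds; the analysis is wrong as written. The cancellation follows from the definition of the change score and needs no assumption: whatever effect exists at 72 hours is subtracted. The 80% power for INF/VV and MSI does not describe the test in SAP 11.4.2.1. With the planned INF/VV effect present at 72 hours and maintained, power for benefit is 2.5% against 81% on the 72-hour value. Under proportional shrinkage the test leans towards placebo.

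Those sizes rest on two-sided 5%, SD in points and a 20% placebo mean; the shrinkage and late-effect ranges also rest on correlations of 0.5–0.9. Power on change can exceed 80% if much of the effect arises after 72 hours and the scans correlate highly, but it is still not the stated figure. Troponin AUC is unaffected. The defect matters most for INF/VV, MSI and INF and must be fixed there; the cardiac function section needs the same correction.

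**What to change.** In SAP 11.4.2.1 and 11.4.2.4:

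- Apply the pooled FDY-5301 vs placebo comparison, with its difference and 95% confidence interval, to observed values at 72 hours and, separately, at 3 months.
- Apply ANOVA/Dunnett to the same values, and name the variable in both sections.
- Correct the sentence with the damaged timepoint phrase.
- Do not use the 72-hour scan as baseline for inference on infarct size. Change from 72 hours to 3 months may stay as a supplementary remodeling analysis.

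State in SAP 9 which timepoint the power refers to, with the placebo means, alpha and sidedness. State how 3-month MSI is derived, since Protocol 10 includes edema imaging only in the 72-hour scan. List any remaining departure from the protocol in SAP 13.

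The cost is SAP wording and table shells, with no new data. Pooled CMR comparisons rise from 7 to 14 (7 parameters × 2 times), or 21 if change is also tested. Dunnett contrasts go to 3 × 14 = 42 on observed values. The repeats by TIMI flow and infarct type grow in proportion. All are secondary and exploratory.
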